4.2. Scientific Rationale for Study Design

VMALS-002-2b is designed as a safety extension study to evaluate the long-term safety profile of Engensis following the main study, VMALS-002-2, which is a well-controlled Phase 2a study in ALS Participants, as it is a double-blind, randomized, placebo-controlled, and multicenter study to evaluate muscle biomarkers and the safety profile of Engensis in Participants with ALS.

4.3. Justification for Dose

No treatments will be administered during this extension study.

4.4. Randomization

There is no randomization in this study.

4.5. End of Study Definition

The end of the study is defined as the date on which the last Participant in the study completes the Day 365 Visit, is terminated, or discontinued early from the study (early termination).

4.6. Study Completion

The study will be considered complete upon Helixmith's approval of the clinical study report.

4.7. Completed Participants

A Participant is considered to have completed the study if the Participant completes the Day 365 Visit.

5. STUDY POPULATION

Participants who complete the Day 180 Visit in VMALS-002-2 are eligible to enroll in this extension study, VMALS-002-2b.

5.1. Number of Participants

The number of Participants to be enrolled in this extension study depends upon the number of Participants who complete the Day 180 Visit in VMALS-002-2 and provide written informed consent for this extension protocol (prior to, during, or after their Day 180 Visit in the VMALS-002-2 study).

5.2. Participant Identification

To maintain confidentiality, the name of the Participant should not be recorded on any study document other than the informed consent form. All Participants who sign the informed consent form will be identified by the same unique identifier/number they were assigned in VMALS-002-2.

5.3. Lifestyle Considerations

5.3.1. Meals and Dietary Restrictions

There are no meal or dietary restrictions for this study.

5.3.2. Caffeine, Alcohol, and Tobacco

There are no caffeine, tobacco, or alcohol restrictions for this study.

5.3.3. Supplements

There are no restrictions on herbal medicines or dietary supplements or changes in their use during the study. The use of any supplements during the study will be recorded on the Participant's medical record and the electronic case report form (eCRF) as concomitant medications.

5.3.4. Activity

There are no restrictions on activity. Participants should be advised to continue their normal activity level during the study.

6. STUDY INTERVENTION

There will be no treatment administered during this study.

6.1. Measures to Minimize Bias

6.1.1. Randomization

There will be no randomization of Participants in this VMALS-002-2b extension study; Participants who are entered into this extension study will continue to be followed in a blinded fashion.

6.1.2. Blinding

Participants, Investigators, Site staff, CRO staff, and Sponsor staff will remain blinded to treatment assignments except for the designated unblinded Clinical Research Associate (CRA) and the unblinded Medical Monitor.

To avoid potential bias, Investigators and study staff are expected to refrain from sharing safety and treatment outcomes with other participating Sites.

The DSMB, independent of the Sponsor, may review individual unblinded Participant narratives in the case of an SAE or multiple SAEs for which the DSMB Chair requests unblinding, but will not have access to unblinded tables and listings unless requested by the DSMB Chair when assessing a potential safety signal. While the study is ongoing and prior to database lock, the datasets will remain blinded with no preliminary summary of the study by the individual treatment arms except when requested by the DSMB Chair.

6.1.3. Maintenance of the Blind

The treatment assignment for each Participant that was determined by the randomization module in the VMALS-002-2 study will be continued for each Participant in the VMALS-002-2b extension study.

IN CASE OF EMERGENCY (i.e., SERIOUS ADVERSE EVENT [SAE]) AND ONLY WHEN THIS INFORMATION INFLUENCES THE PARTICIPANT'S MEDICAL MANAGEMENT, the Investigator may contact the designated unblinded Medical Monitor to request unblinding of the treatment assignment. The date and reason for unblinding will be documented in the electronic data capture (EDC) system.

6.2. Concomitant Therapy

Standard of care for ALS is presented in the American Academy of Neurology (AAN) guideline regarding management and care of the patient with ALS.⁶³ Recommendations are presented for multidisciplinary care, symptom management, and the treatment of cognitive/ behavioral impairment.

6.3. Prior and Concomitant Medications, Treatments, and Procedures

Concomitant medications and procedures during VMALS-002-2b from Day 180 of VMALS-002-2 to Day 365 of this extension study will be recorded on the Medication and

History eCRF on the Days 240, 300, and 365/ET. Any medication or vaccine, including over-the-counter or prescription medicines, vitamins, herbal supplements, and procedures that the Participant is receiving at the time of enrollment or receives during the study must be recorded on the Concomitant Medications or Concomitant Procedures eCRF. For each medication or treatment, the following information will be collected:

- Medication trade or generic name, or procedure name
- Indication for which the medication/procedure was given
- Dose/strength, route, and frequency of administration of medications
- Date started and date stopped (or continuation at study exit)
- Reason for use of concomitant medications or procedures

The medical monitor must be contacted if there are any questions regarding concomitant or prior therapy.

7. DISCONTINUATION OF STUDY INTERVENTION AND PARTICIPANT WITHDRAWAL

7.1. Participant Withdrawal/Discontinuation

Any Participant may voluntarily discontinue the study at any time without prejudice. The Investigator may discontinue a Participant from the study at any time if, in the Investigator's judgment, the Participant's health or safety would be compromised by remaining in the study.

Specific reasons for study discontinuation include the following:

- Participant decision
- Investigator's decision
- TEAEs or TESAEs
- Insufficient compliance with study requirements
- Lost to follow-up
- Other

The specific reasons for Participant discontinuation will be recorded in the eCRFs.

The following assessments will be performed at an Early Termination (ET) Visit, if possible, for Participants who discontinue prior to the Day 365 Visit.

- Complete Physical examination
- Vital signs, weight, height
- 12-lead ECG
- Serum chemistry and hematology
- Concomitant medications and procedures
- ALSFRS-R
- SVC
- HHD
- ALSAQ-40
- PGIC
- CGIC
- TEAEs, TESAEs, and AESIs

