2.3. Benefit/Risk Assessment

2.3.1. Risk Assessment

The risks for the study medication and study procedures are summarized in the following table.

Potential Risk of Clinical Significance	Summary of Data/Rationale for Risk	Mitigation Strategy
Risks of Engensis		
Cancer Patients with melanoma and tongue cancer appear to be at an increased risk of death due to ALS⁶²	Angiogenesis plays an important role in the proliferation and metastatic spread of cancer as these processes are dependent on an adequate supply of oxygen and nutrients and removal of waste products.	Participants who develop any type of cancer during VMALS-002-2 will be followed long-term in VMALS-002-2b
Angiogenesis	Intimal angiogenesis in atherosclerotic plaques contributes to unstable plaque, plaque hemorrhage, and plaque rupture that predisposes to thrombotic or embolic events.	Participants who have experienced a stroke, cerebrovascular accident, or myocardial infarction within 3 months before Screening for VMALS-002-2 and Participants with peripheral artery disease (PAD) or PAD requiring revascularization will be excluded from VMALS-002-2b
Risks of Study Procedures		
Complications of venipuncture (for blood draws for laboratory tests)	Venipuncture complications include minor bruising, hypotension, and syncope.	Incidence of adverse events of bruising, hypotension, and syncope will be closely monitored throughout the study.

Adverse Events in Clinical Studies

Engensis has been well tolerated in all clinical studies conducted thus far in more than 500 Participants. The preponderant adverse events have consisted of mild, transient injection site effects, including itching, erythema, pain, and muscle spasms. Other TEAEs that have been reported were generally mild to moderate. Refer to the IB for a table of AEs that occurred in $\geq 2\%$ of trial Participants.

Five SAEs have been reported to date as possibly related to study treatment:

- Colon cancer in the Phase 1 trial of CLI (assessed by the investigator to be possibly related to study drug and, even though the sponsor noted that the Participant had a history of colon polyps, a relationship to study drug could not be ruled out)
- Peroneal deep vein thrombosis (categorized as possibly related to the study injection) in the Phase 2 trial of CLI. The mechanism by which HGF or VM202 could be causative is not established.

SAEs reported as possibly related in the VMDN-003 trial included:

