8.3.1. Time Period and Frequency for Collecting TEAE and TESAE Information

All TEAEs and TESAEs will be collected after signing informed consent prior to, on, or after Day 180 of the Study VMALS-002-2 until the time that the Participant completes or withdraws consent for VMALS-002-2b (see definition of TEAE, Section [10.2](#)).

All TESAEs will be recorded and reported to the Sponsor or designee immediately and under no circumstance should this exceed 24 hours, as indicated in Section [10.2.5](#), Appendix 2. The Investigator will submit any updated TESAE data to the Sponsor within 24 hours of its availability.

Investigators are not obligated to actively seek TEAEs or TESAEs after conclusion of the study participation. However, if the Investigator learns of any TESAE, including a death, at any time after a Participant has been discontinued from the study, and he/she considers the event to be possibly, probably, or definitely related to the study intervention or study participation, the Investigator must promptly notify the Sponsor.

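### Participants can be discontinued from this untreated safety follow-up because of an adverse event or poor compliance, and the documents do not secure active collection of new events and vital status to Day 365 after such an exit

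*Protocol*

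**What the plan says.** Protocol Section 6: "There will be no treatment administered during this study". Section 7.1 allows voluntary withdrawal and also discontinuation by the Investigator: "The Investigator may discontinue a Participant from the study at any time if, in the Investigator's judgment, the Participant's health or safety would be compromised" (that is, if the participant stayed in). The list introduced by "Specific reasons for study discontinuation include the following" contains TEAEs or TESAEs, the Investigator's decision and "Insufficient compliance with study requirements", next to loss to follow-up and a residual category. The reasons are entered in the eCRF. An early termination visit, which includes TEAEs, TESAEs and AESIs, is held if possible.

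Section 8.3.1 says that TEAEs and TESAEs are collected "until the time that the Participant completes or withdraws consent for VMALS-002-2b". Further on it says: "Investigators are not obligated to actively seek TEAEs or TESAEs after conclusion of the study participation". The duty that remains is conditional: "if the Investigator learns of any TESAE, including a death, at any time after a Participant has been discontinued from the study", and considers it at least possibly related, the Sponsor must be told. Section 8.3.5 keeps known events under follow-up until they resolve, stabilize or are explained, or contact is lost.

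SAP 6.14.1 ends TEAE and TESAE collection only at withdrawal of consent. SAP 6.2.3 censors time to tracheostomy and time to all-cause mortality at the last visit. SAP 6.4 tabulates discontinuation by primary reason, and SAP 6.14.1.4 plans Listing 16.2.7.4 of TEAEs that led to study discontinuation.

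**The concern.** In a treatment study, stopping for an adverse event normally means stopping the drug while observation goes on. Here there is no drug to stop, so discontinuation can only remove observation, and observation is what the study exists to provide.

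The primary endpoints are the incidence of TEAEs, TESAEs and AESIs, and of clinically significant laboratory values. The TEAE definition in Protocol 10.2.1 applies whatever the causal judgement. If a safety event leads to exit and new events are then not sought, the length of observation depends on the outcome being measured. Poor compliance may act in the same way, since a participant with advancing ALS may find visits hard to attend.

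Mortality raises the same problem. A participant who leaves after a safety event and is censored at the last visit may not have the same prognosis as those who remain, so the censoring may be informative.

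**Working it through.** **1. When does collection end for a participant whom the Investigator discontinues and who has not withdrawn consent?**

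| Source | Rule | Consequence |
|---|---|---|
| Protocol 8.3.1, opening sentence | To completion or withdrawal of consent; Section 4.7 defines completion as the Day 365 Visit | Neither has occurred, so collection continues |
| Protocol 8.3.1, closing paragraph | No active search once participation has ended | Active collection stops |
| SAP 6.14.1 | To withdrawal of consent | Collection continues |
| Protocol 7.1 | One early termination visit if possible | Nothing is specified afterwards |
| Protocol 8.3.5 | Known events are followed | Silent on new events |

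The opening and closing text of 8.3.1 cannot both govern this participant. No section sets out a contact, visit or vital-status check up to Day 365 after such an exit.

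**2. What is kept and what can be lost after exit?**

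- The event that led to exit: already counted.
- The course and outcome of events already reported: kept, under 8.3.5.
- A new TESAE or death judged at least possibly related: notified, but only if the Investigator learns of it.
- A new TESAE or death judged unrelated: no assured route into the data.
- A new non-serious TEAE or AESI: no assured route into the data.

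**3. Does the analysis compensate?** Protocol 9.3.1 uses available data without imputation. The adverse event tables in SAP 6.14.1.4 include none described as adjusted for time under observation. SAP 6.2.13 combines early termination data with Day 365. Shortened observation would therefore be hard to see in the tables.

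**4. Scale.** The plan gives no figure to reproduce. Inputs: Day 180 to Day 365 and a maximum of 18 participants (Protocol 1.1; SAP 4). The number of exits and their timing at Day 240 are assumptions.

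- Length of the extension: 365 − 180 = 185 days.
- Lost by one exit at Day 240: 365 − 240 = 125 days; 125/185 = 68%.
- Planned total: 18 × 185 = 3,330 participant-days.
- One exit: 125/3,330 = 3.8%. Two: 250/3,330 = 7.5%. Four: 500/3,330 = 15.0%.
- One participant is 1/18 = 5.6 percentage points of overall incidence. If the outcome after exit is unknown for two or four participants, the proportion with a given event is uncertain by up to 2/18 = 11.1 or 4/18 = 22.2 points.

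**5. Scale for deaths, as illustration only.** In the earlier open-label ALS study (Protocol 2.2.6.1), 1 of 18 died before the 9-month visit and 14 of the remaining 17 died between then and 36 months. Assuming constant hazards:

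- Early: −ln(17/18)/9 = 0.00635 per month. Late: −ln(3/17)/27 = 0.0642 per month.
- 125 days = 125/30.4375 = 4.11 months.
- Risk of death from Day 240 to Day 365, 1 − exp(−hazard × 4.11): 2.6% (early rate) to 23.2% (late rate).
- With four exits, expected deaths outside active follow-up: 4 × 0.0257 = 0.10 to 4 × 0.2319 = 0.93. The chance of at least one is 10% to 65%.

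These hazards come from a small study in which all participants were treated, so they show order of magnitude only.

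**The case against.** The strongest reply is that nothing in the protocol makes an adverse event a trigger for exit. The Investigator may discontinue a participant, on a stated condition about health or safety. The list in 7.1 works at least in part as a set of reason codes, as the presence of loss to follow-up and a residual category shows. On the opening sentence of 8.3.1 and on SAP 6.14.1, a discontinued participant who has not withdrawn consent is still under collection, so the fault may be one loosely worded paragraph. The early termination visit, the continued follow-up of known events, and the contact attempts for missed visits in Section 7.2 all limit the loss. In the earlier ALS study 17 of 18 participants had adverse events (Protocol 1.1), yet 17 completed nine months and the other died. That study's discontinuation rules are not shown, so this is only indicative.

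Most of this stands, and it rules out three stronger readings.

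- A reader might infer that follow-up stops in participants who have safety events. The documents do not say so: exit is optional and known events remain under follow-up.
- A reader might infer that the cancer mitigation in Section 2.3.1 is defeated. That entry reads "Participants who develop any type of cancer during VMALS-002-2 will be followed long-term in VMALS-002-2b". It concerns cancers that arose in the parent study and are already known, and 8.3.5 does not list study exit as a reason to stop following them.
- A reader might infer that the arm with more early events will show a lower incidence of later ones. The event behind an exit is already counted, SAP 6.3 leaves the percentage base open between non-missing observations and the participant population, and the number of exits in either arm is unknown. Neither the direction nor the size of any bias can be stated.

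The objection does not supply a route for new events or vital status after exit, and it does not remove the conflict within 8.3.1.

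**Conclusion.** The point holds as a gap and a conflict in the rules for ending collection. After discontinuation without withdrawal of consent, the documents do not settle whether new TEAEs, TESAEs, AESIs and deaths are actively sought to Day 365. On the less favourable reading, observation of later events depends on earlier safety events, and censoring mortality at the last visit may be informative.

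The size cannot be established from the documents. An exit at Day 240 loses 68% of that participant's extension period, and two such exits would lose 7.5% of planned participant-days; both the number and the day are assumed. No formal safety testing is planned, so the consequence falls on descriptive incidence and survival summaries in at most 18 people, where one participant is 5.6 percentage points. This is an inexpensive improvement that should be made. It is not evidence that the safety results will be wrong.

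**What to change.** 1. **Protocol 7.1.** Keep the list as recorded reason codes. Deleting the TEAE/TESAE entry would undercut the disposition table (Table 14.1.1.1) and Listing 16.2.7.4. Add that discontinuation for any reason other than withdrawal of consent, death or loss to follow-up ends visits and tests only. TEAE, TESAE, AESI and vital-status collection then continues to Day 365 by telephone or record contact.
2. **Protocol 8.3.1 and 8.3.5, SAP 6.14.1.** Reconcile these with 7.1 to this single end of collection. Reserve the paragraph on passive reporting for the time after it.
3. **SAP 6.2.3.** Censor all-cause mortality at the date last known alive, not at the last visit. Tracheostomy is derived from an ALSFRS-R item, so its censoring still has to rest on the last ALSFRS-R assessment unless another source is specified.

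Cost: a protocol amendment, matching SAP edits, possibly consent wording, and a few extra site contacts. The Schedule of Activities has no telephone contact, so one would have to be defined; Section 7.2 already has sites telephoning participants who cannot be reached. Participants remain free to withdraw, Investigators can still stop visits and procedures, and no clinical rule changes.

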7.2. Lost to Follow-up

A Participant will be considered lost to follow-up if he or she repeatedly fails to return for scheduled Visits and is unable to be contacted by the Site between the Day 180 of VMALS-002-2 and the Day 365 (+7 days) of VMALS-002-2b.

The following actions must be taken and recorded if a Participant fails to return to the clinic for a required study Visit:

- The site must attempt to contact the Participant and reschedule the missed Visit as soon as possible. The site must counsel the Participant on the importance of

maintaining the assigned Visit schedule and ascertain whether or not the Participant wishes to and/or should continue in the study.

- If no response is obtained from the Participant, the Investigator is encouraged to contact one of the Participant's relatives or his/her general practitioner.
- Before a Participant is deemed lost to follow up, the Investigator or designee must make every effort to regain contact with the Participant, including at least three telephone calls and, finally, a certified letter to the Participant's last known mailing address. These contact attempts should be documented in the source records.
- Should the Participant continue to be unreachable, the Participant will be considered lost to follow-up.

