2.2.6.1. Phase 1/2 Study in Participants with Amyotrophic Lateral Sclerosis

A Phase 1/2, open label, single center study in 18 Participants diagnosed with clinically definite, clinically probable, or clinically probable-laboratory supported ALS (VMALS-001; NCT02039401) lasting 9 months was completed.⁶¹ Prior to injections on Day 0, Participants were assessed using the ALSFRS-R, the Medical Research Council (MRC) scale for muscle strength testing, dynamometry, forced vital capacity (FVC), and muscle circumference of treated muscles.

All Participants (18 Participants) received a total of 64 mg of Engensis IM in the upper limbs (abductor pollicis brevis, first dorsal interosseous, biceps, deltoid, extensor carpi radialis, flexor carpi ulnaris, and flexor carpi radialis) and lower limbs (quadriceps, gastrocnemius, and tibialis anterior).

Engensis was administered over the course of four visits: Days 0, 7, 14, and 30. As in previous Engensis studies, the final dose of Engensis for each target muscle group was divided and administered 2 weeks apart with injection of the upper limbs at separate visits followed by injection of the lower limbs.

Post-injection, ALSFRS-R, FVC, and muscle strength (determined by the MRC scale) were assessed at Days 30, 60, and 90, and at 6 and 9 months. Muscle circumference and dynamometry were conducted on Days 60 and 90, and at 6 and 9 months. Participants were contacted through 36 months by phone to assess survival.

After Engensis or Placebo injections through Day 30, seventeen (17) Participants completed the 9-month follow-up; one Participant died prior to the 9-month visit. Three (3) Participants completed the study (36-month follow-up), while 14 Participants died following the 9-month visit; all deceased Participants died due to respiratory failure associated with ALS. Four additional serious adverse events (SAEs) that required hospitalization were reported. All deaths and SAEs were classified as unrelated to the study drug. Injection site reactions were limited to pain and/or bruising and none exceeded grade 2 severity.

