
 To determine whether IM administration of Engensis has positive effects on survival in ALS Participants 	
 Time to all-cause mortality compared to Placebo

 To evaluate Quality of Life improvement following Engensis injections in ALS Participants compared to Placebo 	
 Change from Baseline (Day 0) in Quality of Life (QoL) using the ALS Assessment Questionnaire (ALSAQ; with 40 items, ALSAQ 40) on Day 365 for Engensis compared to Placebo

 To evaluate Patient and Clinical Reported Outcome improvement following Engensis injections in ALS Participants compared to Placebo 	
 Patient Global Impression of Change (PGIC) and Clinical Global Impression of Change (CGIC) at Day 365 for Engensis compared to Placebo

4. STUDY DESIGN**4.1. Overall Design**

VMALS-002-2b is a safety extension study following VMALS-002-2 (A Phase 2a, double-blind, randomized, placebo-controlled, multicenter study designed to assess the safety of IM administration of Engensis in Participants with ALS). Following completion of the Day 180 visit in VMALS-002-2 and signing of written informed consent, Participants may be enrolled in this approximately 180-day extension study.

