8.3.5. Follow-up of TEAEs, TESAEs, and AESIs

After the initial TEAE or TESAE report, the Investigator is required to proactively follow each Participant at subsequent Visits/contacts. All TEAEs, TESAEs, and AESIs (see Section 8.3.4) will be followed until resolution, stabilization, the event is otherwise explained, or the Participant is lost to follow-up (as defined in Section 10.2.3, Appendix 2).

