6.2.3 Duration / Study Day / Time

Study day will be calculated as the number of days from first Study Injection in the Study VMALS-002-2:

- date of event – date of first Study Injection + 1, for events on or after first Study Injection in the Study VMALS-002-2
- date of event – date of first Study Injection, for events before first Study Injection in the Study VMALS-002-2

Duration of ALS diagnosis will be presented in months and calculated as (Date of Screening of the Study VMALS-002-2 – Date of Onset of Symptoms +1) / 30.4375.

QMD Ref: Worldwide-TMP-ST-005-7.0 Effective: 12Aug2019	Governing QMD: Worldwide-SOP-ST-001
Confidentiality Statement	

This document is the property of Worldwide Clinical Trials Inc. and may not be duplicated, copied, altered or removed from company without prior approval from Worldwide Quality Assurance or in compliance with Worldwide Standard Operating Procedures.

Worldwide Clinical Trials Controlled Quality Management Document			
 WORLDWIDE CLINICAL TRIALS	Sponsor:	Helixmith Co., Ltd.	
	Protocol Number:	VMALS-002-2b	
STATISTICAL ANALYSIS PLAN. PHASE 2-3-4			

Time to tracheostomy will be calculated as time from date of first Study Injection in the VMALS-002-2 Study to date of first occurrence of ALSFRS-R questionnaire with answer “**0 - Invasive mechanical ventilation by intubation or tracheostomy**” to question “**12. Respiratory insufficiency**” (ASLFRS-R date – date of the first injection +1) presented in days.

Time to all-cause mortality will be calculated as the time period from date of first Study Drug Injection in the Study VMALS-002-2 to date of death within 365 days presented in days (death date – date of the first injection +1).

Both time-to-event endpoints will be censored by date of last visit.

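### SAP 6.2.3 censors survival at the last visit but counts deaths after it, so the mortality curve is distorted for participants whose visits stop before Day 365

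*Protocol*

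**What the plan says.** The protocol lists survival as an exploratory endpoint (Protocol section 3): "Time to all-cause mortality compared to Placebo". SAP 6.2.3 runs the time from first injection in VMALS-002-2 "to date of death within 365 days presented in days". A death does not have to precede the last visit to count. The same section then sets one censoring rule: "Both time-to-event endpoints will be censored by date of last visit". SAP 6.15.7 asks for descriptive statistics and Kaplan-Meier curves on the two studies combined and gives no other rule.

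The extension visits are Days 240, 300 and 365/ET. SAP 6.4 lists the date of last visit as a disposition item, but no date of last contact or date last known alive.

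Protocol 7.2 deals with missed visits: "The site must attempt to contact the Participant and reschedule the missed Visit as soon as possible". Before declaring loss to follow-up, the site must try further, "including at least three telephone calls and, finally, a certified letter to the Participant's last known mailing address". Asking relatives or the general practitioner is encouraged. These attempts are documented in source records; no eCRF field is named.

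**The concern.** The rule treats two participants with the same attendance differently. Suppose both were last seen at Day 240. One dies on Day 320, stays at risk until then and counts as an event. The other is confirmed alive on Day 365 but leaves the risk set at Day 240. Whether the time after Day 240 is used depends on the outcome, and Kaplan-Meier estimation does not allow for that.

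The rule looks like a carry-over from tracheostomy, where it is right, because SAP 6.2.3 takes that event from ALSFRS-R item 12 and nothing can be observed after the last form.

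At stake is the arm comparison on survival. Two arms with the same mortality can show different curves because more survivors stop attending in one of them. In arms this small, a few early stoppers are enough.

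**Working it through.** The documents state no mortality, event or power figure for this endpoint, so there is no plan figure to reproduce.

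**Hand-sized case.** Assume an arm of 9 (the allocation ratio is not given), one death on Day 320, and k survivors last seen on Day 240 but known alive at Day 365. Under the SAP rule, estimated mortality is 1/(9 − k):

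| k | 0 | 1 | 2 | 3 | 4 |
|---|---|---|---|---|---|
| SAP rule | 11.1% | 12.5% | 14.3% | 16.7% | 20.0% |
| Censored at last date known alive | 11.1% | 11.1% | 11.1% | 11.1% | 11.1% |

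With one death in each of two such arms, k = 3 against k = 0 gives 16.7% against 11.1%, a false difference of 5.6 points.

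**True risk, Day 180 to Day 365.** Protocol 2.2.6.1 reports for VMALS-001 that 1 of 18 died before 9 months, 14 died after the 9-month visit and 3 completed 36 months. With 30.4375 days per month (SAP 6.2.3), the window is 185/30.4375 = 6.08 months, from month 5.91 to month 11.99. The same counts support three readings:

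- Early hazard throughout: −ln(17/18)/9 = 0.00635 per month. Risk = 1 − exp(−0.00635 × 6.08) = 3.8%.
- Hazard changing at month 9, with the later one −ln(3/17)/27 = 0.0642 per month. Risk = 1 − exp(−(0.00635 × 3.09 + 0.0642 × 2.99)) = 19.1%.
- One hazard over 36 months: −ln(3/18)/36 = 0.0498 per month. Risk = 1 − exp(−0.0498 × 6.08) = 26.1%.

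**Large-sample estimate under the SAP rule, all deaths captured.** Let A be survival from Day 180 to Day 240, S survival from Day 240 to Day 365, and m the share of survivors last seen at Day 240. The early stoppers leave a risk set of 1 − mS, of whom S(1 − m) survive, so the curve at Day 365 is A × S(1 − m)/(1 − mS).

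| True risk | A | S | m = 20% | m = 30% | m = 40% |
|---|---|---|---|---|---|
| 3.8% | 0.988 | 0.974 | 4.4% | 4.8% | 5.4% |
| 19.1% | 0.988 | 0.819 | 22.6% | 24.9% | 27.8% |
| 26.1% | 0.907 | 0.815 | 29.4% | 31.5% | 34.2% |

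For example, 1 − 0.988 × 0.819 × 0.8/(1 − 0.2 × 0.819) = 22.6%. If the last visit is at Day 300 instead, the 19.1% row becomes 21.6%, 23.3% and 25.5%. A simulation with 9 per arm, true Day 240 to 365 mortality of 20% and 30% with no visit after Day 240 averaged 26.1% under the SAP rule and 19.9% with censoring at the last date known alive.

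**When later deaths are missed.** Keep true mortality at 20%, with 20% or 40% of participants stopping at Day 240. If stopping is unrelated to risk and none of the later deaths are captured, there is no bias (20.0%). If those who stop have 2 to 3 times the hazard and only 0% to 25% of their deaths are captured, the estimate is 12.0% to 18.8%, which is too low. At 50% capture it is 19.2% to 22.1%, so the sign changes near there. At full capture it is 22.8% to 28.2%.

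**The case against.** A reader might infer that mortality will be overstated, and that proof of survival after the last visit is bound to exist. The documents support neither. Protocol 7.2 requires an attempt at contact, aimed at rescheduling; success may lead to a later visit, which moves the censoring date forward. Protocol 8.3.5 does say "the Investigator is required to proactively follow each Participant at subsequent Visits/contacts", but only after an initial TEAE or TESAE report, so it is not a general duty to check survival. The telephone follow-up in Protocol 2.2.6.1 ("Participants were contacted through 36 months by phone to assess survival") belongs to VMALS-001; this protocol schedules none. Capture of deaths is uncertain too. Protocol 8.3.1 does not oblige investigators to seek events actively after participation ends, and Protocol 10.2.2 excludes death from disease progression from the TESAEs. The direction is therefore conditional.

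A second tempting reading is that any missed visit biases the curve. It does not. Someone who misses Day 240 or Day 300 but attends Day 365 is censored at that visit, within its ±7-day window.

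The size should not be pressed either. The allocation and the rate of early stopping are assumed. SAP 6.15.7 is descriptive, and the log-rank code sits under tracheostomy in 6.15.6. With 1 death in 9 the exact 95% interval is 0.3% to 48%, far wider than the artefact. The primary safety tables are untouched.

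What remains is the rule itself. No other passage replaces it, and uncertain capture of deaths is a further reason to collect vital status in the same way for everyone.

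**Conclusion.** The point holds in conditional form. As written, SAP 6.2.3 keeps time after the last visit only for those who die in it. If those deaths are captured, the mortality curve is too high, and higher in the arm with more survivors whose visits stop early. If those who stop are at higher risk and few of their deaths are captured, it can be too low. With full capture and 20% to 40% of survivors last seen at Day 240, the overstatement is 0.6 to 1.6 points at a true risk of 3.8% and about 4 to 9 points at 19.1%. The VMALS-001 counts cannot narrow the true risk beyond 3.8% to 26%. For an exploratory, mainly descriptive endpoint with at most 18 participants, this is a minor to moderate correction.

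**What to change.** - In SAP 6.2.3, split the rule. Censor time to all-cause mortality at the last date the participant is documented alive, capped at Day 365. Keep the date of the last ALSFRS-R as the censoring date for tracheostomy.
- Record vital status and its date as of Day 365 for every participant on the disposition eCRF page, by visit, telephone, relative or physician, as far as consent allows. Irregular last-contact dates alone would leave part of the same asymmetry, because a later death could still be learned of and counted.
- Where Day 365 status cannot be obtained, apply the same cut-off date to deaths and to survival time.

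The cost is a short change to the SAP, one eCRF date field, and a vital-status contact for the few participants without a Day 365 visit. The field is needed because Protocol 7.2 keeps contact attempts only in source records.
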